7.3. PREMATURE DISCONTINUATION FROM STUDY

Study will be prematurely discontinued in any of the following cases:

- Subject's request.
- Any life-threatening (i.e., Grade 4) AE may cause premature discontinuation.
- Systemic hypersensitivity reaction may cause premature discontinuation.
- Any Grade 3 or 4 ADR (defined in Section 9.3) clinically evaluated by the PI and/or Sponsor as warranting subject discontinuation.
- Non-compliance: Subject's non-compliance with study procedures as evaluated by PI and/or Sponsor as warranting subject discontinuation.

- Other reasons regarded by PI as warranting subject's discontinuation.
- Premature study termination as described in Section 7.4.

Subjects who discontinue the study prematurely will be queried whether an AE contributed to their decision.

7.4. PREMATURE STUDY TERMINATION

The study will be prematurely terminated in any of the following cases:

- Recurring serious or severe ADR (defined in Section 9.1) clinically evaluated by PI and/or Sponsor as warranting study termination.
- A decision made by Sponsor and/or IRB/EC and/or local regulatory agency to terminate the study.

7.5. DEVIATION FROM STUDY PROTOCOL

The investigator shall not deviate from the study protocol without first obtaining a written approval from the Sponsor, or its official designee, and if applicable, from the local IRB/EC according to local regulations.

In the event of medical emergencies, the investigator shall use appropriate medical judgment and will remove the subject from any immediate hazard, then notify the Sponsor or its official designee and if applicable, the local IRB/EC, within 2 days, of the type of emergency and course of action taken.

Any other changes to or deviations from the protocol will be made as an amendment to the protocol and must be approved by the Sponsor or its official designee and the local IRB/EC before they can be implemented. Accordingly, the Sponsor will not assume responsibility or liability for any unauthorized deviation from or change to the protocol.

8. INVESTIGATIONAL PRODUCT AND VEHICLE SPECIFICATIONS

8.1. DESCRIPTION OF RZL-012

RZL-012 investigational drug is intended for a single dose in multiple injections into the subcutaneous fat. The injection dosing regimen and technique is crucial for the therapy safety and efficacy.

8.2. FORMULATION, PACKAGING AND LABELING

The RZL-012 drug is a ready to use liquid to be injected to the subcutaneous fat, supplied in a 1 vial kit. 1 vial contains 250 mg/5 mL RZL-012 in formulation F12.

8.3. STORAGE AND STABILITY OF RZL-012 AND VEHICLE

The RZL-012 kit will be stored in the site pharmacy at monitored room temperature conditions (22 ± 7 °C) protected from light. Storage space will be separate, designated and adequately labeled as containing investigational product.

Stability program of RZL-012 is ongoing and site inventory will be managed by the Sponsor according to accumulating stability data. Suitability of the product's expiration date must take into consideration and comply with FIFO (First In First Out) principals.

The storage conditions are summarized in Table 3.

Table 3: RZL-012 Storage Conditions

Storage Conditions	Maximal Storage Duration
Individual vials: Room temperature (15-30 °C)	According to expiration date as will be provided by manufacturer.
* Stability program for RZL-012 is ongoing and site inventory will be managed by the Sponsor according to accumulating stability data.	

8.4. DOSAGE, DISPENSING AND ADMINISTRATION OF RZL-012 AND VEHICLE

8.4.1. Dosage

RZL-012 therapy is available in vials of 250 mg/5mL.

8.4.2. Administration and Instructions for Use

Each individual vial must be kept and handled at room temperature.

The vial should be manually shaken before consumption.

1 mL Luer-lock syringes with RZL-012 solution should be filled with 30 G 1/2" sterile needle as described below:

- Cohort 1 - Dercum's disease subjects:

Nodule of 2-2.9cm diameter -will be injected 2 * 0.1 mL/syringe/nodule

Nodules of 3-3.9cm diameter - will be injected 3 * 0.1 mL/syringe/ nodule

Nodules of 4-8cm diameter - will be injected 4 * 0.1 mL/syringe/ nodule

In total -A maximum of 8* 0.1 mL/syringe/subject.

- Cohort 2 - lipedema subjects:

First 3 subjects: 6*0.1 mL/syringe/leg, a total of 12* 0.1 mL/syringe/subject.

Last 3 subjects: 8*0.1 mL/syringe/leg, a total of 16* 0.1 mL/syringe/subject.

One vial may be used for dosing of one subject. Breached vials will not be re-used for other subjects. Each vial must be placed back into the container. All open vials must be kept until the end of the study for the Sponsor to decide either to discard or return to the Sponsor.

8.5. ACCOUNTABILITY OF RZL-012 AND VEHICLE

The RZL-012 investigational product was manufactured by PharmaCore (USA) and complies with cGMP requirements. Formulation and packing was done by Nextar (Israel) and complies with cGMP requirements.

The RZL-012 investigational product and vehicle will be supplied in kits, in quantities as needed to comply with the treatment of site subjects according to the study protocol.

Site coordinator will notify the Sponsor or its official designee, in a timely manner and no less than 14 working days in advance, of any supply requirements to prevent shortage.

Shipment, storage and inventory documentation will be updated regularly and kept in the investigation files at the site to allow inspection and trace of the supplied product.

9. ADVERSE EVENTS

9.1. ADVERSE EVENT DEFINITIONS

9.1.1. Definition of AE

An AE is defined as any untoward medical occurrence in a clinical investigation subject administered a pharmaceutical product and which does not necessarily have to have a causal relationship with this treatment. An AE can therefore be any unfavorable and unintended sign (including an abnormal laboratory finding, for example), symptom, or disease temporally associated with the use of a medicinal product, whether or not considered related to the medicinal product. This definition includes any abnormalities or anomalies that were not seen at baseline or which worsened during the course of the study, if present at baseline.

9.1.2. Definition of Serious Adverse Event

A SAE is defined as any AE occurring at any dose that results in any of the following outcomes:

- death
- a life-threatening AE, as defined below

- subject hospitalization or prolongation of existing hospitalization
- a persistent or significant disability/incapacity
- a congenital anomaly/birth defect
- important medical event, as defined below

A life-threatening AE is any AE that places the subject, in the view of the investigator, at immediate risk of death from the reaction as it occurred (i.e., it does not include a reaction that, had it occurred in a more severe form, might have caused death).

An important medical event is an AE that may not result in death, be life-threatening, or require hospitalization but may be considered a serious AE when, based upon appropriate medical judgment, may jeopardize the subject and may require medical or surgical intervention to prevent one of the outcomes listed above. It can also include AEs otherwise judged to be serious by either the investigator or the Sponsor.

9.1.3. Definition of Adverse Drug Reaction

AEs associated with the use of investigational product (i.e., probably or possibly related to treatment as defined in Section 9.3) are also termed ADRs.

9.2. ADVERSE EVENT GRADING

AE will be documented and graded according to the National Cancer Institute Common Terminology Criteria for Adverse Events (CTCAE) v4.03 June 14, 2010) (10).

AE that do not appear in the CTCAE will be graded as follows:

- Mild (Grade 1): Sign or symptom, usually transient, requiring no special treatment and generally not interfering with usual activities.
- Moderate (Grade 2): Sign or symptom, which may be ameliorated by simple therapeutic measures, may interfere with usual activity.
- Severe (Grade 3): Sign or symptom that is intense or debilitating and that interferes with usual activities and/or requires hospitalization. Recovery is usually aided by therapeutic measures and the discontinuation of the study product may be required.
- Life-threatening or disabling (Grade 4): Sign or symptom that is life-threatening or disabling.
- Death (Grade 5): Death related to AE

9.3. CAUSALITY ASSESSMENT OF ADVERSE EVENTS

All AEs will be evaluated by the investigator and assigned an estimated relationship to the RZL-012 investigational product. The terms "probable", "possible", "unlikely", or "unrelated" refer to the association with the use of the investigational product, as defined below in Table 4.

Medical judgment should be used to determine the relationship, considering all relevant factors, including pattern of reaction, temporal relationship, confounding factors such as concomitant medication, concomitant diseases and relevant history.

Assessment of causal relationship should be recorded directly in subjects' CRF.

Definition of AEs causality is specified in the table below (Table 4).

Table 4: Definition of Causality

TERM	DEFINITION	CLARIFICATION
Unrelated	This category applies to those AEs which, after careful consideration, are clearly due to extraneous causes (disease, environment, etc.)	
Unlikely Related	In general, this category can be considered applicable to those AEs, which after careful medical consideration at the time they are evaluated, are judged to be unrelated to the study procedures/investigational product.	
An AE may be considered unlikely related if or when (must have two):
 
 ▪ It does not follow a reasonable temporal sequence from the study procedures/administration of the investigational product. ▪ It could readily have been produced by the subject's clinical state, environmental or toxic factors, or other modes of therapy administered to the subject. ▪ It does not follow a known pattern of response to the study procedures/investigational product.
Possibly Related	This category applies to those AEs for which, after careful medical consideration at the time they are evaluated, a connection with the study procedures/investigational product administration appears unlikely but cannot be ruled out with certainty.	
An AE may be considered possibly related if or when (at least two of the following):
 
 ▪ It follows a reasonable temporal sequence from study procedures/administration of the investigational product. ▪ A causal relationship to the experimental treatment cannot necessarily be reasonably excluded and an alternative explanation (e.g., concomitant investigational product or concomitant disease) cannot be reasonably suggested as causing the treatment emergent AE. ▪ It follows a known pattern of response to the study procedures/ investigational product.
Probably Related	This category applies to those AEs which, after careful medical consideration at the time they are evaluated, are felt with a high degree of certainty to be related to the study procedures/investigational product.	
An AE may be considered probably related if or when (at least three of the following):
 
 ▪ It follows a reasonable temporal sequence from study procedures/administration of the investigational product. ▪ It could not be reasonably explained by the known characteristics of the subject's clinical state, environmental or toxic factors, or other modes of therapy administered to the subject. ▪ It disappears or decreases on cessation or reduction in dose. There are important exceptions when an adverse event does not disappear upon discontinuation of the investigational product, yet investigational product-relatedness clearly exists. ▪ It follows a known pattern of response to the study procedures/investigational product.

TERM	DEFINITION	CLARIFICATION
Definitely Related	This category applies to those AEs which, after careful medical consideration at the time they are evaluated, are felt with definite certainty to be related to the study procedures/investigational product.	An AE may be considered definitely related if or when all of the following apply: 
 ▪ It follows a reasonable temporal sequence from study procedures/administration of the investigational product. ▪ It could not be reasonably explained by the known characteristics of the subject’s clinical state, environmental or toxic factors, or other modes of therapy administered to the subject. ▪ It disappears or decreases on cessation or reduction in dose. There are important exceptions when an adverse event does not disappear upon discontinuation of the investigational product, yet investigational product-relatedness clearly exists. ▪ It follows a known pattern of response to the study procedures/investigational product.

*In this protocol, Unlikely is deemed as Unrelated.

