**Induration — the measured local reaction at the greatest single diameter beyond the injected area surface of all injections (For Dercum's disease – nodules of 2-2.9 cm diameter 2*2 cm, nodules of 3-3.9 cm diameter 3*2 cm nodules of 4-8 cm diameter 4*2 cm. For lipedema -12*2 cm for the first subjects, 15*2cm for the following subjects and 16*2cm for the last subjects), the measurement should be recorded as a continuous variable.

Liver Enzyme Abnormalities Table

Serum *	Mild (Grade 1)	Moderate (Grade 2)	Severe (Grade 3)	Potentially Life Threatening (Grade 4)
Liver Function Tests –ALT, AST increase by factor	3 x ULN	3 – 5 x ULN	5-10 x ULN beyond 10 days	> 10 x ULN beyond 10 days

Study discontinuation is to be considered by the investigator in any case of an intolerable side effect and the actions taken are to be fully documented in source documents and Case Report Forms (CRFs).

To be considered an intolerable side effect, such an event must be considered to be possibly or probably related to the study drug.

Subjects experiencing an intolerable side effect will be withdrawn from the study, but followed for toxicity.

The study may also be prematurely terminated in any of the following cases:

- Recurring serious or severe ADR clinically evaluated by PI as warranting study termination.
- A decision made by Sponsor and/or IRBEC and/or local regulatory agency to terminate the study.

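### Table 4 has a 'Definitely Related' level that the definitions of adverse drug reaction and intolerable side effect leave out, so on a literal reading the most certain reactions are not counted

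*Protocol*

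**What the plan says.** - **Protocol 9.3, Table 4** lists five levels: unrelated, unlikely, possibly, probably and definitely related. The last is for events that "are felt with definite certainty to be related to the study procedures/investigational product".
- **Protocol 9.3, opening text** names four causality terms (probable, possible, unlikely, unrelated). 'Definite' is not among them.
- **Protocol 9.1.3** defines adverse drug reactions (ADRs) as events "probably or possibly related to treatment as defined in Section 9.3".
- **Protocol 3.3.2**, and the synopsis in the same words, define an intolerable side effect as a treatment-related ADR of the required grade and add that "such an event must be considered to be possibly or probably related to the study drug".
- **Protocol 10.5.4 and SAP 5.8.13** analyse the incidence of intolerable side effects, overall and by cohort, with an exact two-sided 95% binomial interval. **Protocol 3.3.1** lets a cohort continue only while at most one of its subjects has had such an event.
- **The SAP** plans a frequency table of intolerable side effects (Table 14.4.1-2) and a table of adverse events by relationship (Table 14.4.1-5). It does not define or group the causality levels.
- **Possibly versus unlikely, Table 4.** 'Possibly Related' covers a connection that "appears unlikely but cannot be ruled out with certainty". 'Unlikely Related' covers events that "are judged to be unrelated to the study procedures/investigational product". The footnote adds: "In this protocol, Unlikely is deemed as Unrelated".

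**The concern.** The investigator's causality label decides whether an event enters the primary incidence and the proceed rule. A programmer who derives the endpoint from the protocol as written would select 'possibly' and 'probably' and omit the strongest level. The site would face the same question when counting affected subjects in a cohort.

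The ADR definition has other uses: the discontinuation and termination provisions (7.3, 7.4), reporting and follow-up of graded ADRs (9.5.1), and expedited reporting, which takes relatedness from 9.1.3 (9.5.3). The same gap carries into each.

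The second, smaller matter is that one counted category is described with the word that names a category not counted.

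**Working it through.** The plan states no figure on this point, so there is none to reproduce. The check compares the passages, then works out the scale of one event.

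**1. Levels side by side**

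| Level | Table 4 | Opening text of 9.3 | ADR (9.1.3) | Intolerable side effect (synopsis, 3.3.2) |
|---|---|---|---|---|
| Unrelated | listed | named | not counted | not counted |
| Unlikely | listed, treated as unrelated | named | not counted | not counted |
| Possibly | listed | named | counted | counted |
| Probably | listed | named | counted | counted |
| Definitely | listed | not named | not mentioned | not mentioned |

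Neither document mentions the fifth level in the two definitions.

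**2. Are the levels nested?** Table 4 uses four criteria: temporal sequence (T), no other explanation (A), improvement on cessation or dose reduction (D) and known pattern (P). Score each 1 if present and 0 if absent.

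- Possibly: T + A + P ≥ 2
- Probably: T + A + D + P ≥ 3
- Definitely: T + A + D + P = 4

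An event with all four present meets all three rules. By its criteria it would also qualify as 'Probably Related'. It falls outside the definitions only once it is recorded as 'Definitely Related'.

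**3. Do 'Possibly' and 'Unlikely' overlap?** Let k = T + A + P. 'Possibly' needs k ≥ 2. 'Unlikely' needs at least two of the three absent, that is 3 − k ≥ 2, or k ≤ 1. Exactly one of the two holds for every k. This assumes that the criteria of the two levels are read as complements; their wording is close to that but not identical.

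**4. Scale of one event.** Inputs: 6 subjects per cohort and 12 in all (10.3); exact binomial interval (10.5.4). The Clopper-Pearson limits for x of n are the 2.5% quantile of Beta(x, n − x + 1) and the 97.5% quantile of Beta(x + 1, n − x). The lower limit is 0 when x = 0.

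| Affected subjects | Estimate | Exact 95% interval |
|---|---|---|
| 0/6 | 0% | 0% to 45.9% |
| 1/6 | 16.7% | 0.4% to 64.1% |
| 2/6 | 33.3% | 4.3% to 77.7% |
| 1/12 | 8.3% | 0.2% to 38.5% |
| 2/12 | 16.7% | 2.1% to 48.4% |

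One subject moves a cohort estimate by 1/6 = 16.7, about 17, percentage points, and the overall estimate by 1/12 = 8.3 points. If two subjects in a cohort have qualifying events and one is coded 'Definitely Related', the literal count falls from 2/6, where the condition for continuing is not met, to 1/6, where it is.

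**The case against.** **It looks like a drafting gap.** The definitions match the four terms in the opening text of 9.3, and the fifth row of Table 4 is the outlier. Section 9.1.3 introduces ADRs as events associated with the product, which can be read as a minimum threshold, and the levels nest as shown. Many investigators would count a definite reaction anyway, and the case report form, which cannot be seen here, may offer only four choices. All of this is plausible, and nothing suggests an intent to exclude. It does not settle the text: either the fifth level is in use and the definitions omit it, or it is not in use and Table 4 is wrong.

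**The level may seldom be used.** Treatment is a single dose, so improvement on cessation or dose reduction is hard to judge, although Table 4 allows exceptions. This bears on frequency, not on the contradiction.

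**A reader might infer that definite reactions would go unseen.** The documents do not support that. Section 10.2.1 adds adverse events to the primary endpoint with no causality condition. Adverse events are tabulated by relationship, serious events are reported whatever their relationship (9.5.2), and the dose-level decision in cohort 2 follows review of all safety data by the principal investigator and the Medical Monitor (3.3.1). What is affected is the analysed incidence and the formal count.

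**A reader might also infer that the line between possibly and unlikely is undefined.** That goes too far. 'Unlikely Related' records a conclusion of no link and 'Possibly Related' records remaining doubt. The footnote refers to the category label, and the criteria separate the two levels. What stands is a clash of words. It is worth repairing because the criteria only say how an event may be considered and so do not plainly override the definition.

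**Conclusion.** Wrong as written. Table 4 has five causality levels, while the opening text of 9.3, the ADR definition and the intolerable-side-effect condition stop short of the fifth, and the SAP does not close the gap. On a literal reading, a Grade 3 or greater event that meets the other conditions but is coded 'Definitely Related' is left out of the incidence in 10.5.4 and out of the cohort count.

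The effect on results cannot be estimated, because the documents give neither event rates nor the share of events likely to be coded at that level. The 17-point shift is the weight of any single subject in a cohort of 6, not an estimate of bias. The conclusion assumes that the form offers all five levels and that the definitions are applied as worded.

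The possibly/unlikely wording is an editorial point only.

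**What to change.** 1. Reconcile the synopsis, 3.3.2, 9.1.3 and the opening text of 9.3 with the five levels of Table 4, so that the ADR definition and the analysed endpoint do not omit the most certain level. The intolerable-side-effect definition also triggers subject withdrawal and governs whether a cohort continues. Those responsible for clinical conduct therefore need to settle that wording; this review does not propose the rule.
2. Add one sentence at SAP 5.8.13 stating which Table 4 levels count as related when the incidence is derived. This alone is not enough: SAP 5.8.6 lets the SAP supersede the protocol only for data handling and analysis, so it cannot settle the proceed rule.
3. Reword the 'Possibly Related' definition to match its listed criteria and avoid the name of a category treated as unrelated. Do not simply delete the phrase about an unlikely link: the present sentence is inclusive, and deletion could narrow the category and lower the safety count.

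The cost is a few words in four protocol passages, one definition sentence in Table 4 and one sentence in the SAP, with the usual amendment steps. It needs no new data and no change to the sample size.

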9.4. UNEXPECTEDNESS OF ADVERSE DRUG REACTIONS

An ADR is considered unexpected when its nature or severity is not consistent with the applicable product information (i.e., RZL-012 Investigator's Brochure).

9.5. ADVERSE EVENT REPORTING AND MONITORING REQUIREMENTS

9.5.1. General

All AEs, serious and non-serious, will be fully documented in both source documents and CRFs as described in Section 6.1.13, and each AE will be assessed in light of its clinical significance. For each AE, the investigator will provide the onset, end, intensity, treatment required, outcome, seriousness and action taken with the investigational drug. The investigator will determine the relationship to the investigational drug, i.e., causality assessment, for each AE.

Any AE occurring prior to initiation of first dose, after initiation of the first dose and or during any point throughout the study should be recorded on the AE page of the CRF. All AEs occurring until subject is terminated from the study (28 days after the injection of RZL-012 and in the highest dose cohort until 6 months from injection of RZL-012), should be captured in the CRF. AEs should be recorded in the CRF using the medical terminology found in the source documentation. Whenever possible, diagnoses should be given when signs and symptoms are due to a common etiology.

Occurrence of any Grade 4 and Grade 3 or 4 ADR must warrant clinical evaluation by the treating investigator and reported to the Sponsor within 7 calendar days.

ADRs graded > 1 will be followed-up until resolution, or for a maximal duration of 6 months after RZL-012 injection, whichever occurs first.

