
Visit Schedule (See Table 2)
	
Subject site visits will be performed \pm 1 day from scheduled date for study visits Day 0-28 and $2\pm$ 1 days from schedule date for follow-up visits (Day 56). All data relevant for the visit needs to be obtained within 3 days (e.g., blood tests results) of visit.
 
Screening Day visit (Day -14 through -2):
 
 - Following signing the informed consent - assessment of subject eligibility will include: medical history, physical examination, vital signs, ECG, serology assays (HBV, HCV and HIV), clinical laboratory tests, drug screen. 
Clinical laboratory tests will include:

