6.2.1. Screening Procedures

All information collected and documented during screening procedures will be reviewed to ensure eligibility in reference to study inclusion and exclusion criteria, and fully documented in subject file.

Screening visit should be performed no later than 2 days prior to baseline visit for all cohorts.

Study Screening Day procedures will include the following:

- Informed Consent - Section 6.1.1
- Medical History - Section 6.1.2
- Concomitant Medication - Section 6.1.3
- Physical Examination - Section 6.1.4
- Pain Measurement – Section 6.1.5
- QOL Measurement –Section 6.1.6
- Vital Signs and Measurements - Section 6.1.5
- Serology Assays – Section 6.1.8
- Clinical Laboratory Tests - Section 6.1.9
- ECG - Section 6.1.10

- Draize Score – Section 6.1.11
- Photography of Injected Site – Section 6.1.12
- Leg Circumference – Section 6.1.12
- Ultrasound – Section 6.1.12

Subjects may be rescreened if they were screened and not dosed within 14 days. The following procedures will be performed: Clinical Laboratory Tests (hematology, serum chemistry, and urinalysis), vital signs, Draize score and photography.

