6.2.4. Baseline Visit

Baseline visit is defined in the study as Day 0. Baseline visit will be performed to complete screening evaluation, and to review all procedures necessary to confirm subject eligibility. Subjects will stay under supervision in the study center till 8h + 3h following drug injection.

Screening information may be considered for baseline data if acquired within the adequate timeframe as described in Table 2.

Table 2: Subject Information and Timeframes

Information	Timeframe	Follow-up Timeframe
Informed Consent Form	Signed prior to any study dedicated procedure	
Medical History and Concomitant Medications	At Screening Day visit	
Physical examination	At Screening Day visit and at Day 28	
Pain Measurement	At Screening Day visit and at Days 14, 28	At Day 56
QOL Measurement in lipedema subjects	At Screening Day visit and at Days 14, 28	At Day 56
Vital Signs	At Screening Day visit and at Days 0 (pre and following injection), 1, 7, 14, 21, 28	
Pulse rate	At Day 0 (following injection) and at Day 1	
ECG	At screening Day 1 visit, at Day 0 (following injection) and at Days 1, 14, 28	
Draize Score at the Injected Site	At Screening Day and at Days 0 (pre- and following injection), 1, 7, 14, 21, 28	At Day 56
Serology assays (HbSAg, HCV and HIV)	At Screening Day visit	
Drug screen	At Screening Day visit	
Serum chemistry and Hematology	At Screening Day and at Day 1, 3, 7, 14 and 28	
Urinalysis	At Screening Day visit and at Days 14 and 28	

Information	Timeframe	Follow-up Timeframe
Ultrasound for nodules quality and size. Fat thickness – for lipedema	At Screening Day visit and at Day 28	At Day 56
Ultrasound for nodules size and selection for injection	At Days 0 (pre- injection)	
Photography of the Injected Sites	At Screening Day visit and at Days 1, 7, 14, 21, 28	At Day 56
AE Assessment	At Days 1, 3, 7, 14, 21, 28	At Day 56

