10.2. STUDY ENDPOINTS

10.2.1. Primary Safety Endpoints

The primary safety endpoint is the incidence of intolerable side effects and AEs.

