5.8.16 Safety and Tolerability

5.8.17 Safety analyses will be descriptive in nature.

5.8.18 All reported AEs will be coded to a standard set of terms using MedDRA coding dictionary (V22.0 or higher) treatment.

	DOCUMENT NUMBER: 050-BST-PLN-001	PAGE: 19 of 24
TITLE: Statistical Analysis Plan of Protocol Number RZL-012-FD-P2aUS-001		EFFECTIVE DATE : 02/05/2019 REVISION NUMBER : 1.0

5.8.19 AEs and tolerability data will be presented descriptively by treatment and cohort. AEs will be tabulated by body system, preferred term, seriousness, severity and relation to study drug by cohort. Where applicable, changes in values over time (e.g., lab values, vital signs, ECGs) will be presented; this will include clinical laboratory evaluations (including CBC, blood chemistry and urinalysis), coagulation (INR, PTT and PT), cytokines, vital signs, and ECGs. Shift tables of normal / abnormal versus baseline may be presented as well.

5.8.20 Draize scores will be presented in tabular format by visit, treatment, and cohort.

5.8.21 Concomitant medication verbatim terms (as recorded on the CRFs) will be coded to Anatomical Therapeutic Chemical (ATC) Level 2 and 4 using the World Health Organization (WHO) dictionary.

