14.4 Safety Data and Other Assessments

14.4.1 Adverse Events

Table 14.4.1-1: Frequency of Any Adverse Events

	DOCUMENT NUMBER: 050-BST-PLN-001	PAGE: 22 of 24
TITLE: Statistical Analysis Plan of Protocol Number RZL-012-FD-P2aUS-001		EFFECTIVE DATE : 02/05/2019 REVISION NUMBER : 1.0

Table 14.4.1-2: Frequency of any intolerable side effects

Table 14.4.1-3: Summary of Adverse Events by SOC and PT by treatment

Table 14.4.1-4: Summary of Adverse Events by SOC, PT, severity and by treatment

Table 14.4.1-5: Summary of Adverse Events by SOC, PT, relationship to study treatment and by treatment

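### AEs that start before the injection are recorded with post-dose AEs, and the SAP's AE tables have no treatment-emergent rule to keep them out

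*Protocol*

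**What the plan says.** **Recording.** Protocol 9.5.1 requires "Any AE occurring prior to initiation of first dose, after initiation of the first dose and or during any point throughout the study" to be entered on the AE page of the CRF. In the synopsis, the visit schedule has the entry "Screening Day visit (Day -14 through -2", with injection on Day 0. Section 6.2.1 adds: "Subjects may be rescreened if they were screened and not dosed within 14 days".

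**Analysis.** SAP 5.8.18 covers coding: "All reported AEs will be coded to a standard set of terms using MedDRA coding dictionary (V22.0 or higher) treatment". SAP 5.8.19 covers tabulation: "AEs will be tabulated by body system, preferred term, seriousness, severity and relation to study drug by cohort". The first shell is "Table 14.4.1-1: Frequency of Any Adverse Events". Tables 14.4.1-3 to -5 summarise AEs by SOC and PT, then by severity and by relationship, each by treatment. SAP 5.4.3 confirms that every subject receives RZL-012. Neither document defines a treatment-emergent AE for analysis. The term occurs once, undefined, in the causality table of protocol section 9.3.

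**Endpoint.** Protocol 10.2.1 states: "The primary safety endpoint is the incidence of intolerable side effects and AEs". The synopsis names only intolerable side effects, and 10.5.4 and SAP 5.8.13 give the exact confidence interval for those alone.

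**Schedule.** The AE row of protocol Table 2 reads "At Days 1, 3, 7, 14, 21, 28", with Day 56 as follow-up. Appendix I also appears to start AE assessment at Day 1. The synopsis has AEs recorded after treatment on Day 0.

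**The concern.** An AE table in a single-arm trial is read as what happened after the drug. If pre-injection events share the CRF page and nothing in the SAP separates them, a subject whose only event is a cold during screening counts as having an AE in the sole treatment column. There is no control arm against which background events could be judged.

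The denominators are small. SAP 5.8.2 presents results overall, by cohort and by cohort and dose, so single subjects matter. Section 10.2.1 makes AE incidence part of the primary safety endpoint, so the counting rule should be fixed before the data are tabulated.

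**Working it through.** The plan states no figure for this point, so there is none to reproduce. The check is a trace through the text followed by an illustration of size.

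**1. Does anything in the plan remove a pre-dose event?**

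- The safety set (protocol 10.4.1, SAP 5.7.1 and 5.7.2) selects subjects who were injected. It filters subjects, not events.
- The AE definition (protocol 9.1.1) refers to a subject given a product and to findings not seen at baseline or worsened since. It conflicts with 9.5.1, but it says what an AE includes and sets no onset cut-off for a table.
- Protocol 9.5.2 limits SAE reporting to events after injection. No such line is drawn for AE tabulation.
- Table 14.4.1-5 splits AEs by relationship, which is not a secure filter. The causality table in 9.3 judges relation to study procedures as well as to the product. A screening venepuncture bruise follows a procedure in time and is a known response to it, which meets two criteria for possibly related. The lead-in to 9.3 mentions only the product, so the rating could go either way.
- Intolerable side effects (protocol 3.3.2) must be Grade 3 or greater, with listed exceptions left to discussion, and possibly or probably related to the study drug. A pre-dose event should not qualify.

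**2. Share of collection time before the drug.** Formula: pre / (pre + post). The pre-dose gap is 2 to 14 days, assuming that recording starts at the screening visit; rescreening can lengthen it. The post-dose period is 56 days (6.1.15) or 28 days, with 6 months for the highest dose cohort (9.5.1; taken here as 182 days).

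| Post-dose days | 2-day gap | 14-day gap |
|---|---|---|
| 56 | 2/58 = 3.4% | 14/70 = 20.0% |
| 28 | 2/30 = 6.7% | 14/42 = 33.3% |
| 182 | 2/184 = 1.1% | 14/196 = 7.1% |

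**3. Weight of one subject.** A subject whose only AE is pre-dose moves incidence by 1/6 = 16.7 points in a cohort, 1/12 = 8.3 points overall, and 1/3 = 33.3 points in a lipedema dose group of three.

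**4. Expected pre-dose events (illustration).** The documents give no background rate. Assume 0.2 to 1.0 AE per subject per 28 days, constant, and a full 14-day gap.

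- Mean per subject: rate × 14/28 = 0.1 to 0.5.
- Events in 12 subjects: 12 × 0.1 = 1.2 to 12 × 0.5 = 6.0.
- Subjects with at least one: 1 − exp(−0.1) = 9.5% to 1 − exp(−0.5) = 39.3%.

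**5. Net effect on any-AE incidence (illustration).** Only subjects with no post-dose AE add to the count, so, assuming independence, inflation = (1 − P(post-dose AE)) × P(pre-dose AE).

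- If 90% of subjects have a post-dose AE (an assumption): 0.1 × 9.5% = 1.0 point to 0.1 × 39.3% = 3.9 points. In 12 subjects this is about 0.1 to 0.5 of a subject.
- If post-dose AEs arise only from background at 0.5 per 28 days: 1 − exp(−1.0) = 63.2% over 56 days becomes 1 − exp(−1.25) = 71.3% with the 14 pre-dose days, a rise of 8.1 points.

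The SOC/PT and severity tables lack this masking at the any-AE level: a pre-dose event in a term with no post-dose event adds directly to that row.

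**The case against.** The case on the other side is substantial, and much of it stands.

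- A reader might infer that the SAP orders all reported AEs to be tabulated. It does not: that phrase belongs to the coding sentence, and the tabulation sentence says only AEs. Shell bodies and footnotes are not in the text available, so a filter there cannot be excluded. Even so, the sentences and titles that can be read carry no onset condition, and 9.5.1 expressly puts pre-dose events among the data.
- A reader might infer that the primary safety result is compromised. The documents do not support that. The synopsis and the primary analysis concern intolerable side effects, which require a drug relation. Only the AE wording in 10.2.1 brings the primary endpoint in.
- A reader might infer that Day 0 reactions would be lost because Table 2 starts at Day 1. The synopsis and 9.5.1 both cover events after injection on Day 0. The row lists assessment visits, so this is a schedule mismatch.
- A reader might take 20% of collection time, or 9.5% to 39.3% of subjects, as the distortion. The first assumes a full 14-day gap against 56 days. The second ignores subjects who also have a post-dose AE, and injection-site reactions are expected (7.2). No AE assessment is scheduled before Day 1, so pre-dose events are probably under-collected and the expected counts in step 4 are likely too high.
- Onset is collected for every AE and all AEs are listed (Listing 16.2.6-1), so events dated before Day 0 can be separated at analysis. This stands, except on Day 0 itself: section 6.1.15 asks for a start date, not a time.

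None of this supplies a counting rule. It limits the size of the problem.

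**Conclusion.** The concern holds at moderate severity. Read literally, the plan counts pre-injection events in the any-AE, SOC/PT, severity and relationship tables and in the AE component of 10.2.1. The intolerable-side-effect incidence and its exact interval should be essentially unaffected.

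The size cannot be fixed from the documents. Against 56 post-dose days, pre-dose time is 3.4% to 20.0% of collection time, and one affected subject is worth 16.7 points in a cohort. At the assumed rates, the net change in any-AE incidence is a few points where post-dose AEs are common, and larger where they are not. These estimates assume a constant background rate, recording from screening, and equal ascertainment before and after dosing; the last is doubtful given the visit schedule.

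**What to change.** 1. In SAP 5.8.19, and for Tables 14.4.1-1 and 14.4.1-3 to -5, count only AEs with onset, or worsening in grade, at or after the first injection on Day 0.
2. Show pre-injection events in a separate listing.
3. Record onset time for events on Day 0, so that they can be placed before or after the injection.
4. Reconcile protocol 9.1.1, 9.5.1, the synopsis entry on Day 0 post-treatment AEs, and the AE row of Table 2 and Appendix I.
5. The definition also needs one end day. The documents give 56 days (6.1.15) and 28 days or 6 months (9.5.1), and these should be reconciled at the same time.

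The cost is one SAP definition, one listing and one time field on the AE page, plus text alignment. No visit or subject is added. SAP 5.8.6 already lets the SAP govern how data are handled, so the counting rule can be placed there.
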